7.7 Concomitant and other treatments

7.7.1 Concomitant medications

Concomitant medications are any prescription or over-the-counter preparations, including herbal products and “natural remedies”, used by a patient while participating in this clinical study.

For all concomitant medications, an indication for its use should be provided. If the stated indication is a non-specific condition, e.g. “rash”, documentation of the condition, as specific as possible, should be maintained in the patient’s clinical study records as source documentation.

7.7.1.1 Statins

When coadministered with roxadustat, hydroxymethylglutaryl coenzyme A reductase inhibitor (statin) exposure was increased 2- to 3-fold. For patients randomized to roxadustat, investigators should consider this interaction and local prescribing information when deciding on the appropriate statin dose for individual patients, bearing in mind the impact of ethnicity, other concomitant medications, renal and hepatic function. Goals of lipid lowering treatment should be maintained as clinically indicated. The recommended maximum daily statin doses are: simvastatin 20 mg, atorvastatin 40 mg, rosuvastatin 10 mg, pravastatin 40 mg, fluvastatin 40 mg (20 mg if eGFR<30), pitavastatin 2 mg (1 mg if eGFR<30).

7.7.1.2 Phosphate binders

When coadministered with phosphate binders, roxadustat exposure was reduced. Patients should be advised to discuss with the investigator before changing their phosphate binder dose or dosing time. To optimize absorption of roxadustat, subjects should take roxadustat with at least 1 hour separation from their phosphate binder.

7.7.1.3 Herbal medicine

Use of herbal medicine during the study is not prohibited but strongly discouraged. All herbal and natural remedies should be reviewed by the investigator and if considered safe, may be allowed to continue at the same dose.

7.7.2 Prohibited medications

The following treatments/medications are prohibited during the study:

- Any other investigational drug: from randomization until EOS.
- Any erythropoietin analogue during the treatment period except for study medication or rescue medication (see Section 7.7.4.2)
- Iron-chelating agents (e.g. deferoxamine/desferrioxamine, deferiprone, or deferaxirox therapy): from 4 weeks prior to screening until EOS
- Androgens: from randomization onwards until EOS
- Dapsone (at any dose) from randomization onwards until EOS
- Chronic doses of acetaminophen/paracetamol >2.0 g/day from randomization until EOS

7.7.3 Supplemental iron use

Oral iron supplementation is allowed for both treatment arms without restriction. Oral iron is recommended for dietary supplementation to support erythropoiesis and as the first line for prevention and treatment of iron deficiency, unless the patient is intolerant to this route of treatment.

In subjects receiving roxadustat, the investigator may initiate the use of an approved IV iron supplement if:

- A patient's Hb level has not sufficiently responded to two or more dose increases of study drug, and
- Ferritin <100 ng/ml or transferrin saturation (TSAT) <20%

Study treatment may continue during IV iron administration. Discontinuation of IV iron supplementation is recommended once the patient is no longer considered to be iron deficient (ferritin >100 ng/mL and TSAT >20%). Use of IV iron will be recorded in the eCRF. In subjects receiving epoetin alfa, IV iron supplementation will be given according to standard of care.

In addition to scheduled assessments (Table 1) iron indices may be assessed anytime (via central lab) to evaluate iron storage status of the patients, if considered necessary by the investigator.

7.7.4 Rescue therapy guidelines

Rescue therapy guidelines are provided to optimize the standardization of rescue therapy by investigators and to ensure the safety of individual study patients. Rescue therapy should be recorded in the eCRF.

7.7.4.1 Red blood cell transfusion

Red blood cell (RBC) transfusion is allowed in either roxadustat or epoetin alfa treated patients if rapid correction of anemia is required to stabilize the patient's condition (e.g., acute hemorrhage)

or the investigator is of the opinion that the blood transfusion is a medical necessity. Study drug treatment may continue during or after RBC transfusion administration. Transfusion will be recorded in the eCRF.

7.7.4.2 Erythropoietin analogue administration in patients randomized to roxadustat

For patients randomized to roxadustat, the investigator may initiate use of an approved erythropoietin analogue if all of the following criteria are met:

- A patient's Hb level has not sufficiently responded to two or more dose increases or the maximum dose limit of the study drug has been reached, and
- The patient's Hb is <8.5 g/dL on two consecutive measurements drawn at least five days apart; and
- Clinical judgment does not suggest iron deficiency or bleeding as a cause of lack of response or rapid decline in Hb (see 7.7.4.1 and 7.7.4.2 above for addressing these conditions), and
- Reducing the risk of all immunization in transplant eligible patients and/or reduction of other RBC transfusion-related risks is a goal

The patient is not allowed to be administered both an erythropoietin analogue and study drug at the same time. Treatment with an erythropoietin analogue should be stopped when Hb >9 g/dL or after a 4-week cycle has been completed, whichever comes first. Study treatment should be resumed after the following intervals:

- Two days after stopping epoetin
- One week after stopping darbepoetin alfa
- Two weeks after stopping methoxy polyethylene glycol-epoetin beta (Mircera)

If more than one cycle of erythropoietin analogue rescue is required, the investigator should permanently discontinue study drug. Use of erythropoietin analogues will be recorded in the eCRF.

Note: For patients randomized to epoetin alfa, the investigator may initiate use of a different erythropoietin analogue if clinically indicated. Use of the different erythropoietin analogue will be recorded in the eCRF and will be considered rescue therapy.

7.7.4.3 Therapeutic Phlebotomy

If there are clinical concerns for a patient due to excessive elevation in Hb levels, the investigator may decide to perform a therapeutic phlebotomy instead of, or in addition to, a dose hold. This should be documented and discussed with the study AstraZeneca study physician.

7.7.5 Other concomitant treatment

Other medication than described above, which is considered necessary for the patient's safety and well-being, may be given at the discretion of the Investigator and recorded in the appropriate sections in the eCRF.

7.8 Post Study Access to Study Treatment

After end of treatment with study drug, patients should be managed according to local standard of care.

8. STATISTICAL ANALYSES BY ASTRAZENECA

8.1 Statistical considerations

Analyses will be performed by AstraZeneca or its representatives. A comprehensive SAP will be prepared prior to database lock. It is recognized that Regulatory Authorities might require different efficacy and/or safety endpoints or alternate analyses for approval. The endpoints and analyses described in this protocol are intended for the US (FDA) submission. Regional SAPs will fully describe any changes to endpoints or analyses that differ from those described in this protocol.

8.2 Sample size estimate

Primary efficacy variable: With at least 600 subjects, the study will provide at least 99% power to demonstrate non-inferiority of roxadustat versus epoetin alfa for the primary efficacy endpoint (i.e., Hb change from baseline to the average level during the evaluation period defined as Week 28 until Week 52). This assumes a difference (roxadustat minus epoetin alfa) of -0.30 g/dL, a non-inferiority margin for this difference of -0.75 g/dL and a standard deviation of 1.25 g/dL.

To contribute adjudicated CV events for the pooled CV analyses across the phase 3 program: approximately 2000 subjects will be randomized in a 1:1 ratio to either roxadustat or active control, i.e. epoetin alfa. The sample size for this study is driven by the overall requirement of adjudicated CV events for the phase 3 program in dialysis-treated CKD subjects (which consists of four studies in total targeting 611 subjects with MACE events). The three other studies in the study program are FG-4592-064, 1517-CL-0613, FG-4592-063.

Further information related to the sample size determination can be found in the study statistical analysis plan and the pooled statistical analysis plan.

8.3 Definitions of analysis sets

8.3.1 Intention to Treat Analysis Set (ITT)

All subjects who have been randomized to study treatment will be included irrespective of their protocol adherence and continued participation in the study. Subjects will be analysed according to their randomized study medication irrespective of intake of study medication.

8.3.2 Per Protocol Set (PPS)

All randomized subjects without important protocol deviations and who have received at least 8 weeks of study treatment and have valid corresponding Hb measurements from the central laboratory will be included in the PPS. Subjects will be analysed according to their randomized study medication irrespective of intake of study medication. Subjects with an important protocol deviation will be included in the PPS up to the time point when the violation was met. For criteria for PPS exclusion, see Table 1 in the SAP. Further details of important protocol deviations are available in a Protocol Deviation Plan. Subjects will be censored at the earliest of date of an important protocol deviation, the EOS visit, or last intake of study drug.

8.3.3 Safety analysis set (SAS)

All subjects who received at least one dose of randomized study drug will be included in the Safety Analysis Set. Throughout the safety results sections, erroneously treated subjects will be accounted for in the actual treatment group. If a subject has received both treatments, only the initial period will be utilized. On-treatment analyses will be emphasized.

8.3.4 Full Analysis Set (FAS)

The FAS consists of all subjects in the ITT analysis set who received at least one dose of study drug and have baseline and at least one post-dose Hb assessment. If actual study medication received differs from the randomized treatment arm, the randomized treatment arm will be used for analysis for the FAS. This analysis set is primarily used for EX-US submissions

8.3.5 Subjects who will not be included in any analysis sets

Subjects or sites identified prior to Database lock (breaking of Sponsor blindness, open-label study) with major Good Clinical Practice violations and where the integrity of the data is strongly questioned through thorough independent investigations will be excluded from all analyses and all analysis sets. This includes but are not limited to subjects who have been identified to be part of a potential fraud investigation, subjects who have not signed an informed consent, subjects randomized in error (e.g. a subject considered to be a screen fail but by mistake randomized in the IWRS due to a technical error). Further, subjects being randomized more than once will only contribute to the analysis one time. These patients will be analyzed according to their first assigned randomization number and treatment code. All AE's reported for the subjects will be assigned to the subject's first randomization number. All subjects excluded from all analysis sets will be properly documented

8.4 Outcome measures for analyses

8.4.1 Primary efficacy endpoint:

US FDA: The primary efficacy endpoint is the mean change from baseline in Hb averaged over week 28 to week 52. A multiple imputation approach with analysis of covariance (ANCOVA) will be applied as a method to handle missing data. Details of the ANCOVA multiple imputation are provided in the SAP.

Hb results obtained from the central laboratory will be used for all Hb efficacy analyses. Baseline Hb is defined as the mean of the three last central laboratory Hb values from the screening and randomization visits.

Hb values under the influence of a rescue therapy will not be censored.

EU health authorities: The primary efficacy endpoint is the mean change from baseline in Hb averaged over week 28 to week 36, without having received rescue therapy (i.e. RBC transfusion for all subjects or ESA for subjects treated with roxadustat) within 6 weeks prior to and during this 8-week evaluation period.

8.4.2 Hb related secondary efficacy endpoints:

The Hb related secondary efficacy endpoints are:

- The EU primary endpoint is the first secondary efficacy endpoint.
- Mean change in Hb from baseline to the subjects mean level between week 28 to week 52 in subjects with baseline high-sensitivity C-reactive protein (hsCRP) greater than the Upper Limit Normal (ULN)
- Proportion of total time of Hb ≥ 10 g/dL from week 28 to week 52. The proportion of total time will be computed as follows: For each subject, the recorded Hb values will first be linearly interpolated between measurements. The time this interpolated curve is ≥ 10 g/dL will be computed and subsequently divided by the time between the measurements at week 28 and week 52. Patients without any Hb measurements from week 28 will not be considered for this variable.
- Proportion of total time of Hb within the interval of 10-12 g/dL from week 28 to week 52. The proportion of total time will be computed as follows: For each subject, the recorded Hb values will first be linearly interpolated between measurements. The time this interpolated curve is within 10-12 g/dL will be computed and subsequently divided by the time between the measurement at week 28 and week 52. Patients without any Hb measurements from week 28 will not be considered for this variable.

8.4.3 Lipid related secondary efficacy endpoints

To evaluate the roxadustat effect on lipids, the following variable will be evaluated

- Mean change from baseline in LDL cholesterol to week 24.

8.4.4 IV iron related secondary efficacy variable endpoints:

The use of IV iron will be investigated with the variable:

- Average monthly IV iron use per subject during, week 36 to EOS (monthly defined as a period of 4 weeks).

8.4.5 Rescue therapy related secondary efficacy endpoints:

The need for rescue therapy will be evaluated as

- Time-to-first (and proportion of subjects receiving) administration of red blood cell (RBC) transfusion as rescue therapy (rescue therapy guidelines are specified in the CSP, Section 7.7.4).

8.5 Adjudicated CV Events Analyses for Safety Assessments

The CV events described in Section 5.2.1 will be adjudicated by the Independent Event Review Committee (IERC) according to the IERC charter. The same adjudication committee will be used for four phase 3 studies, FG-4592-064, 1517-CL-0613, FG-4592-063, and D5740C00002, in the CKD-DD program. Analyses of these adjudicated events are described in a separate pooled analysis plan.

8.6 Methods for statistical analyses

A detailed Statistical Analysis Plan (SAP) will be finalized prior to database lock. Any significant changes to the analyses described in this protocol will be highlighted in the SAP and the Clinical Study Report (CSR). Moreover, further details of the statistical analyses are provided in the SAP.

8.6.1 Stratification variables

The randomization in this study will be stratified by country. The stratification variables for the other two studies in the program will be used in the analyses for this study as covariates, with addition of incident vs stable dialysis. The stratification variables are:

1. Baseline Hb (≤ 10.5 g/dL vs > 10.5 g/dL)
2. cardiovascular/cerebrovascular/thromboembolic medical history (Yes vs. No)
3. geographical region (US vs. Ex-US)
4. incident vs. stable dialysis (dialysis duration ≤ 4 months vs > 4 months from the randomization date)

Baseline Hb will be included in the analyses as a continuous covariate, hence, not as a dichotomous factor, unless specified otherwise. Throughout this document, the variable

cardiovascular/cerebrovascular/thromboembolic medical history will be shortened as CV history, and the variable incident vs stable dialysis will be shortened as dialysis duration

CV history at baseline will be defined for subjects with history of any of the following diseases:

- Myocardial infarction
- Percutaneous coronary intervention
- Coronary artery bypass
- Cardiac failure congestive
- Ischaemic stroke
- Haemorrhagic stroke
- Cerebrovascular accident

8.6.2 Analysis of the primary efficacy endpoint for US

Mean change in Hb from baseline to the subjects mean level from week 28 to week 52 will be analyzed with multiple imputation ANCOVA as described in the SAP. The model will contain terms for the baseline Hb measurement, treatment arm, CV history, geographic region and dialysis duration. Non-inferiority of roxadustat compared to epoetin alfa will be declared, and this test as successful, if the lower bound of the 2-sided 95% confidence interval of the difference between roxadustat and epoetin alfa exceeds -0.75 g/dL. The ITT analysis set will be used.

8.6.3 Analysis of the primary efficacy endpoint for EU (Secondary Endpoint for FDA)

The primary efficacy endpoint for EU is Hb change from baseline (BL) to the average Hb of weeks 28 to 36, without having received rescue therapy (i.e. RBC transfusion for all subjects and ESA for roxadustat subjects) within 6 weeks prior to and during this 8-week evaluation period and will be analysed using MMRM. The model will contain terms for the baseline Hb measurement, treatment arm, visit, visit by treatment, CV history, geographic region and dialysis duration. Data up to visit of Week 52 will be included in the model. Non-inferiority of roxadustat compared to epoetin alfa will be declared, and this test as successful, if the lower bound of the 2-sided 95% confidence interval of the difference between roxadustat and epoetin alfa exceeds -0.75 g/dL. The PPS will be used for non-inferiority. In addition to the comparison based on the PPS population, to address the formal test for non-inferiority, results will also be provided based on the FAS population, to allow also for a potential superiority comparison. The latter test is not part of the formal testing sequence.

8.6.4 CV safety endpoint analyses

The CV safety evaluation strategy is to conduct pooled analyses of adjudicated data across the study program to ensure that the overall number of events is high enough to provide adequate power. Thus, all analyses of CV safety will be conducted in accordance with the PSAP.

8.6.5 Analysis of the secondary efficacy endpoints

Secondary efficacy endpoints will be tested using a fixed sequence approach to adjust for multiple testing. If the p-value from a test is less than 0.05, the test will be declared as successful and the analysis will continue to the next comparison in the sequence. Formal statistical hypothesis testing will be stopped as soon as a test is accompanied by a p-value ≥ 0.05 . The PPS will be used on the first secondary endpoint for non-inferiority, on treatment analysis will be used on the secondary endpoint related to RBC transfusion as rescue therapy, and the ITT analysis set will be used for all the remaining secondary endpoints.

1. The EU primary endpoint for non-inferiority is the first secondary efficacy endpoint for FDA (see above).
2. Mean change from baseline in LDL cholesterol to week 24 will be analysed using ANCOVA. Baseline Hb and baseline LDL will be used as covariates and treatment groups, CV history, geographic region and dialysis duration as fixed effects. Superiority will be declared if the upper bound of the 2-sided 95% confidence interval of the difference between roxadustat and epoetin alfa exceeds 0.
3. Mean change in Hb from baseline to the subjects mean level from week 28 to week 52 in subjects with baseline hsCRP greater than the Upper Limit Normal (ULN) will be analysed analogously as the primary efficacy endpoint. Superiority of roxadustat compared to epoetin alfa will be declared, and this test as successful, if the lower bound of the 2-sided 95% confidence interval of the difference between roxadustat and epoetin alfa exceeds 0 g/dL.
4. Proportion of total time of interpolated Hb values ≥ 10 g/dL from week 28 until week 52 will be estimated for each subject and used as dependent variable. The difference between roxadustat and epoetin alfa will be compared using ANCOVA. Baseline Hb will be used as a covariate and the treatment groups, CV history, geographic region and dialysis duration as fixed effects. Non-inferiority between the groups will be declared, and this test as successful, if the lower bound of the 2-sided 95% confidence interval of the difference between roxadustat and epoetin alfa exceeds -0.15.
5. Proportion of total time of interpolated Hb values within the interval 10-12 g/dL from week 28 until week 52 will be estimated for each subject and used as dependent variable. The difference between roxadustat and epoetin alfa will be compared using ANCOVA. Baseline Hb will be used as a covariate and the treatment groups, CV history, geographic region and dialysis duration as fixed effects. Non-inferiority between the groups will be declared, and this test as successful, if the lower bound of

the 2-sided 95% confidence interval of the difference between roxadustat and epoetin alfa exceeds -0.15.

6. The average monthly IV iron use during Week 36 to EOS will be compared between the two treatment groups using a Wilcoxon Rank Sum test. Superiority will be declared if the p-value is less than 0.05.
7. Time-to-first (and proportion of subjects receiving) RBC transfusion as rescue therapy. The baseline Hb, geographic region, dialysis duration and CV history will be included as covariates.

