3.1.6.5 Other exploratory variables

- Variables concerning serum iron profiles: Iron, TIBC, Ferritin and TSAT. Mean value at each time-point tested, and change from baseline.
- Variables concerning lipids: total cholesterol, high-density lipoprotein (HDL) and triglyceride: mean values and change from baseline at each timepoint tested; percent of subjects who achieved target LDL level <100 mg/dL, at each timepoint ; subgroup analyses on patients on statins and those not on statins
- Variables concerning heart rate and blood pressure: heart rate, systolic blood pressure (SBP), diastolic blood pressure (DBP) and mean arterial pressure (MAP).
- Variables concerning concomitant medication: Usage of statins and types of statins, initiation of ESA therapy post study drug discontinuation
- Change from baseline in hepcidin to week 24.

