4.2.2 Confirmatory analysis for the efficacy endpoints

To address the issue of multiple testing while maintaining the overall type-I error, adopting a 5% two-sided significance level, a closed testing sequence will be used for the efficacy endpoints. First, the primary efficacy endpoint analysis according to Section 0 will be performed. If successful, the testing will continue with the secondary efficacy endpoints in the order as specified in Section 4.3.4. Confirmatory statistical hypothesis testing will continue until the first statistically non-significant treatment difference is observed. However, treatment comparisons following and including the first non-significant comparison will be examined in an exploratory manner.

All analyses other than part of this confirmatory analysis will be interpreted descriptively. Consequently, no adjustments for multiplicity will be necessary for such analyses. Ninety-five percent confidence intervals will be calculated, where appropriate, as measures of study precision. P-values may be calculated but are to be regarded as descriptive.

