4.3.4 Secondary efficacy endpoints analyses

Secondary efficacy endpoints will be tested using a fixed sequence approach to adjust for multiple testing. If the p-value from a test is less than 0.05, the test will be declared as successful and the analysis will continue to the next comparison in the sequence. Formal statistical hypothesis testing will be stopped as soon as a test is accompanied by a p-value ≥ 0.05 . The PPS will be used for the first secondary endpoint for non-inferiority, OT+3 analysis set will be used for the secondary endpoints related to RBC transfusion as rescue therapy, and the ITT analysis data set will be used for all the remaining secondary endpoints.

1. The EU primary endpoint for non-inferiority is the first secondary efficacy endpoint for FDA (see above).

2. Mean change from baseline in LDL cholesterol to week 24 will be analysed using ANCOVA. Baseline Hb and baseline LDL will be used as covariates and treatment groups, CV history, geographic region and dialysis duration as fixed effects. Superiority will be declared if the upper bound of the 2-sided 95% confidence interval of the difference between roxadustat and epoetin alfa falls below 0.
3. Mean change in Hb from baseline to the subjects mean level from week 28 to week 52 in subjects with baseline hsCRP greater than the Upper Limit Normal (ULN) will be analysed analogously as the primary efficacy endpoint. Superiority of roxadustat compared to epoetin alfa will be declared, and this test as successful, if the lower bound of the 2-sided 95% confidence interval of the difference between roxadustat and epoetin alfa exceeds 0 g/dL.
4. Proportion of total time of interpolated Hb values ≥ 10 g/dL from week 28 until week 52 will be estimated for each subject and used as dependent variable. The difference between roxadustat and epoetin alfa will be compared using ANCOVA. Baseline Hb will be used as a covariate and the treatment groups, CV history, geographic region and dialysis duration as fixed effects. Non-inferiority between the groups will be declared, and this test as successful, if the lower bound of the 2-sided 95% confidence interval of the difference between roxadustat and epoetin alfa exceeds -0.15.

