5. Proportion of total time of interpolated Hb values within the interval 10-12 g/dL from week 28 until week 52 will be estimated for each subject and used as dependent variable. The difference between roxadustat and epoetin alfa will be compared using ANCOVA. Baseline Hb will be used as a covariate and the treatment groups, CV history, geographic region and dialysis duration as fixed effects. Non-inferiority between the groups will be declared, and this test as successful, if the lower bound of the 2-sided 95% confidence interval of the difference between roxadustat and epoetin alfa exceeds -0.15.
6. The average monthly IV iron use during Week 36 to EOS will be compared between the two treatment groups using a Wilcoxon Rank Sum test. Superiority will be declared if the p-value is less than 0.05.
7. Time-to-first (and proportion of subjects who received) RBC transfusion as rescue therapy, will be analysed using Cox proportional hazard model. The baseline Hb, geographic region, dialysis duration and CV history will be included as covariates. Non-inferiority will be claimed, and this test successful, if the upper bound of the 2-sided 95% CI for the hazard ratio (roxadustat/epoetin alfa) is less than or equal to 1.8.

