6. CHANGES OF ANALYSIS FROM PROTOCOL

There are no changes of analysis from protocol version 8.0, 19 September 2018.

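### The protocol's LDL superiority rule points the wrong way, and the SAP states the opposite rule while reporting no change from the protocol

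*Protocol*

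**What the plan says.** Both documents place LDL change to week 24 second among seven ordered secondary tests. They use the same ANCOVA and covariates, the same 95% interval and the ITT set. They differ only in the success rule.

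- Protocol 8.6.5, item 2: "Superiority will be declared if the upper bound of the 2-sided 95% confidence interval of the difference between roxadustat and epoetin alfa exceeds 0".
- SAP 4.3.4, item 2, declares superiority if the "upper bound of the 2-sided 95% confidence interval of the difference between roxadustat and epoetin alfa falls below 0".

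The opening paragraph of protocol 8.6.5 also sets a general condition for every secondary test: "If the p-value from a test is less than 0.05, the test will be declared as successful and the analysis will continue".

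Protocol 8.6 undertakes to flag significant changes of analysis in the SAP and in the study report. SAP section 6 states: "There are no changes of analysis from protocol version 8.0, 19 September 2018". SAP Table 4 lists changes from SAP Edition 3.0 only and does not mention the direction of the LDL rule.

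On the direction of benefit, SAP 3.1.6.5 includes the "percent of subjects who achieved target LDL level <100 mg/dL, at each timepoint", so a low value is the goal. The protocol's version history also describes this endpoint as one of lipid reduction.

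**The concern.** If lower LDL is the benefit and the difference is roxadustat minus epoetin alfa, a benefit is a negative difference, and superiority needs the whole interval below 0. The protocol instead asks for an upper bound above 0. An interval straddling 0 meets that condition, and so does one lying wholly above 0. An interval lying wholly below 0, the only one that shows a reduction, fails it.

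A claim under multiplicity control therefore has opposite decision rules in the two governing documents, and the SAP tells the reader that they agree. If the direction is put right without a record, a reader comparing the study report with the protocol could ask whether the rule was turned round after the data were seen.

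**Working it through.** **Inputs.** The two-sided 5% level is from SAP 4.2.2. The only subtraction order the documents give is roxadustat minus epoetin alfa, stated for hemoglobin in protocol 8.2 and SAP 4.1.3. I assume that it applies to LDL. The documents give no LDL effect, standard deviation or power, so there is no LDL figure to reproduce, and effects are expressed in standard errors (SE).

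**The rules as conditions on Z.** Let Z = estimated difference / SE and k = true difference / SE. The upper bound is above 0 exactly when Z > −1.96.

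- Protocol sentence alone: Z > −1.96, probability 1 − Φ(−1.96 − k).
- SAP rule: Z < −1.96, probability Φ(−1.96 − k).
- Protocol sentence together with two-sided p<0.05: Z > +1.96, probability 1 − Φ(1.96 − k).

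The first two are complements. Apart from an upper bound of exactly 0, every data set meets one and fails the other.

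**Results.** The value 3.24 = 1.96 + 1.28 is chosen because it gives the SAP rule 90% power.

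| True difference (k) | Protocol sentence alone | SAP rule | Protocol sentence and p<0.05 |
|---|---|---|---|
| 0 | 0.975 | 0.025 | 0.025 |
| −3.24 (LDL lower on roxadustat) | 0.100 | 0.900 | about 0.0000001 |
| +3.24 (LDL higher on roxadustat) | >0.999 | about 0.0000001 | 0.900 |

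The 0.025 in the last column of the first row arises entirely from trials in which LDL is significantly higher on roxadustat.

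**Illustration at the planned size.** Assume a standardised effect d (difference / SD) and no missing data, so that k = d / √(2/n) with n per arm.

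- n = 1000, d = −0.1: k = −0.1/0.0447 = −2.24. SAP rule 0.609, protocol sentence 0.391.
- n = 1000, d = −0.2: k = −4.47. SAP rule 0.994, protocol sentence 0.006.
- n = 300, d = −0.2: k = −0.2/0.0816 = −2.45. SAP rule 0.688, protocol sentence 0.312.

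**Reversed subtraction order.** Suppose the difference were epoetin alfa minus roxadustat. A benefit would be positive, and superiority would need the lower bound above 0. The protocol sentence would still be met 97.5% of the time with no true difference. Combined with p<0.05 it would reduce to a correct rule, but the SAP sentence would then be met only when LDL is significantly higher on roxadustat. So under either order one of the two documents points the wrong way.

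**The case against.** The strongest reply is that this is a slip already put right where it counts. The latest SAP entry is dated 28 September 2018, after protocol 8.0 of 19 September, and protocol 8.6 refers to the SAP for further detail. Item 3 of the same protocol list uses a correctly directed bound for hemoglobin, so the intent is plain. Only significant changes have to be flagged, and correcting an evident error may not be one. The 97.5% comes from one sentence read without the p<0.05 condition. The subtraction order for LDL is not written down.

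Much of this stands. The analysis as executed would probably follow the SAP and be right. The 97.5% describes the sentence alone, not the whole section, and the subtraction order is an assumption.

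Three things remain. On the only order the documents give, the p<0.05 condition restores the 2.5% error rate but in the wrong direction, so a real LDL reduction could never be called superior. The protocol sentence read alone is not a superiority rule under either order. And SAP section 6 does not record a correction; it says that nothing differs.

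**Conclusion.** The concern holds. Protocol 8.6.5, item 2, states a reversed criterion for a confirmatory secondary endpoint, SAP 4.3.4 states its complement, and SAP section 6 leaves the difference undeclared. With no true effect, the two sentences declare superiority with probability 0.975 and 0.025. With a true reduction of 3.24 SE, the figures are 0.100 and 0.900. These rest on a normal approximation, on lower LDL being the benefit, and on the difference being roxadustat minus epoetin alfa.

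The consequence is confined to the LDL claim. Progression to steps 3 to 7 is set by p<0.05 in the opening paragraph, so I do not claim that the reversed inequality opens or blocks them. The primary hemoglobin endpoint and its sample size are untouched. This should be fixed as a correction of the documents, not as a change of analysis.

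**What to change.** In protocol 8.6.5, item 2, require the upper bound to fall below 0, and define the difference as roxadustat minus epoetin alfa. If the protocol is not amended, list the corrected LDL rule in SAP section 6 as a departure from protocol 8.0 and carry it into the study report.

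An optional clarification could go in at the same time; the finding does not depend on it. SAP 4.2.2 says: "Confirmatory statistical hypothesis testing will continue until the first statistically non-significant treatment difference is observed". That fits non-inferiority steps poorly. Protocol 8.6.5, SAP 4.2.2 and SAP 4.3.4 could instead say that testing proceeds only when a step meets its own stated criterion. For IV iron the SAP says only "Superiority will be declared if the p-value is less than 0.05", so the direction favouring roxadustat could be added. Protocol item 7 gives no criterion and could refer to SAP 4.3.4, item 7, where the upper hazard-ratio bound must not exceed 1.8.

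The cost is one phrase in the protocol or one line in the SAP, plus a sentence or two if the clarification is taken up. No new data or analyses are needed.
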